MEDICAL UNIVERSITY OF SOUTH CAROLINA

Study Protocol

**A Proof of Concept Study of Inhaled Nitric Oxide for Adults
with Pulmonary Non-Tuberculous Mycobacterial Infection**

IND Number: 140649

Date and Version of Protocol: October 01, 2019

(Version 3.0)

NCT #: 03748992

IRB approved on 18SEP2018

Title	A Proof of Concept Study of Inhaled Gaseous Nitric Oxide (gNO) for Adults with Pulmonary Non-Tuberculous Mycobacterial (NTM) Infection
Clinical Phase	Phase 2
Objective	To evaluate the efficacy and safety of open-label exposure of gNO in patients with NTM lung disease
Endpoints	
Primary
 
 • Culture growth (positive or negative) at end of treatment (EOT) compared to baseline 
Secondary
 
 • Safety and tolerability assessments based on adverse events (AEs), clinical values (i.e., methemoglobin levels) • Semiquantitative mycobacterial culture results comparing EOT to baseline 
Exploratory
 
 • Time to positive mycobacterial cultures comparing EOT to baseline • Measures of systemic inflammation comparing EOT to baseline • Absolute change in quality of life scores from baseline to EOT
Study Population	Adult subjects with NTM lung disease and persistently positive mycobacterial sputum cultures
Number of Subjects	10
Number of sites	2
Study Duration	Subjects will be treated for 3 weeks (5 days per week) and followed monthly for 3 months
Study Design	This 2 study is designed to evaluate the efficacy and safety of open-label gNO treatment in subjects with NTM lung disease and persistently positive sputum cultures growing NTM. This is a proof-of-concept study in which all subjects will be treated with gNO (i.e. no control) to see if there can be a microbiological effect by conversion to negative sputum cultures and how long that effect can be sustained following treatment. In addition, this study will assess the feasibility of such a treatment course in this patient population and measure relevant clinical outcomes (e.g. cough, quality of life). Subjects will provide sputum for culture at baseline, weekly during treatment, and monthly for 3 months following treatment to assess if there is persistence of infection in cultures. Safety measures will include monitoring of arterial oxygen saturation and methemoglobin levels. All serious and non-serious adverse events will be collected
Assessments	
 • Feasibility: ability to recruit subjects, ability to complete the planned treatment, and assessment of their experience and willingness to undergo this therapy • Efficacy: sputum cultures (mycobacteria), symptom scores (cough, quality of life) • Safety: AEs, clinical monitoring assessments (pulse oximetry), vital signs, and physical examinations
Statistical Analyses	Data will be summarized descriptively for each subject. The overall response rates (culture conversion short and long term) will be calculated after each patient has completed the trial, and exact binomial confidence intervals will be constructed.

SCHEDULE OF ASSESSMENTS

Table 3-1: Schedule of Assessments

Visit	Screening	Treatment Period									Follow up Period		
		A1	A2-4	A5	B1	B2-4	B5	C1	C1-4	C5	F1	F2	F3
Day	-28-14	1	2-4	5	8	9-11	12	15	16-18	19	W7	W11	W15
Informed consent	x												
Medical history	x												
Demographics ^a	x												
Physical examination	x	x			x			x			x	x	x
Height and weight	x				x			x			x	x	x
Vital signs	x	x	x	x	x	x	x	x	x	x	x	x	x
Symptom score ^b	x			x			x			x	x	x	x
Safety labs ^c	x									x			
CRP	x									x			
Spirometry ^d	x	x ^d			x ^d			x ^d					
Sputum cultures ^e	x			x			x			x	x	x	x
Echocardiogram	x												
Pulse oximetry	x	x	x	x	x	x	x	x	x	x	x	x	x
MetHb measurement	x	x	x	x	x	x	x	x	x	x			
gNO dosing		x	x	x	x	x	x	x	x	x			
Adverse events		x	x	x	x	x	x	x	x	x	x	x	x
Concomitant medications	x	x	x	x	x	x	x	x	x	x	x	x	x

^a Demographics include sex, race, and age. Baseline characteristics include diagnosis, and if CF include *CFTR* genotype

^b Symptom scores will include cough score (Leicester), quality of life (SGRQ, CFQ-R, QOL-B), as appropriate for the underlying diagnosis (i.e. CF subjects will complete the CFQ-R and SGRQ; other subjects will complete the QOL-B and SGRQ)

^c Safety labs include comprehensive metabolic panel (to include creatinine, AST, ALP, ALT and chemistry), complete blood cell count with differential, GGT, PT/INR, 6-GPD level, and urine pregnancy test (if applicable)

^d Spirometry will be performed pre and post first treatment of the day

^e Sputum will be tested for bacteria and mycobacteria (including AFB smear and culture). Susceptibility testing will not be performed

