9.1.2 Treatment Period (Days 1-15)

The treatment period is separated over 3 weeks (A, B, and C) each with 5 days of treatment, and 2 days off treatment in between. On the first day of each treatment week (A1, B1, C1) subjects will be evaluated for any changes in health or medications. They will undergo physical examination, including height and weight. They will undergo measurement of efficacy outcomes (symptom scores) as per the Study Assessment Schedule (Table 3-1). During each day of treatment (A1-A5, B1-B5, and C1-C5), subjects will be exposed to gNO through a tight-fitting mask at 160 ppm for 50 minutes for each treatment. There will be three treatments given on each day, with 3 hours between each treatment. The subjects will be monitored with pulse oximetry throughout their exposure to gNO to assess SaO₂ and metHb levels. On the last day of each treatment period (A5, B5, C5), the subjects will repeat their symptom scores as well as provide sputum for mycobacterial culture.

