10.2 Exclusion Criteria

Subjects will be excluded if they have any of the following:

- Smoking history in the prior 6 months
- Significant hemoptysis within 30 days prior to screening (>5 ml of blood in one coughing episode or >30 ml of blood in a 24 hour period)
- Forced expiratory volume at one second (FEV₁) <40% of predicted
- On supplemental oxygen or SaO₂ <90% at screening or Day 1, or within 30 days prior to enrollment.
- Known cardiac (left heart) insufficiency (defined as LVEF <35%) prior to screening
- Known pulmonary hypertension
- Known or suspected hemoglobinopathy
- Initiation of NTM treatment regimen or a change in the regimen was made in the prior 6 months. Subjects on active treatment can be enrolled if they have been on a stable anti-NTM regimen for at least 6 months.
- Initiation of new chronic therapy within 4 weeks prior to screening
- Use of drugs known to increase methemoglobin (see 12.2.7) at screening
- Any of the following abnormal lab values at screening:
 - 6-GPD deficiency
 - Hemoglobin <10g/dl
 - Platelet count <100,000/mm³
 - Prothrombin time international ratio (INR) >1.5
 - Abnormal liver function defined as any two of the following
 - ALT >3x ULN
 - AST >3x ULN
 - ALP >3x ULN
 - GGT >3x ULN
 - Abnormal renal function defined as:
 - Calculated Creatinine Clearance <50 ml (as calculated by Cockcroft/Gault)
- For women of child bearing potential:
 - Positive pregnancy test at screening or
 - Lactating or
 - Unwilling to practice a medically acceptable form of contraception from screening to Day 15 (acceptable forms of contraception: abstinence, hormonal birth control, intrauterine device, or barrier method plus a spermicidal agent)
- Use of an investigational drug within 30 days prior to screening
- Intravenous or oral steroids (>10 mg/d prednisone equivalent) in the 14 days prior to screening
- Any condition that the Investigator believes would interfere with the intent of this study or would make participation not in the best interest of the subject.

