11 DOSING OF STUDY DRUG

11.1 General Dosing Information

Gaseous NO (5000 ppm), delivered with air as carrier to dilute it to 160 ppm, will be administered by inhalation for 50 minutes three times daily on Days 1-5, 8-12, and 15-19. On each day, treatment will be given with a minimum of 3 hours between the end of one treatment and the start of the following treatment. Subjects will receive 160 ppm during each 50 minute inhalation period (daily exposure 400 ppm hours). This will result in a total of 6000 ppm hours of exposure.

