Sputum will be collected for culture at Screening, and Days 5, 12, and 19 (treatment dates), and Weeks 7, 11 and 15 (follow up). Sputum samples will be processed at the MUSC clinical laboratory, using standard decontamination procedures, fluorochrome microscopy, solid medium culture on a biplate of Middlebrook 7H10 agar with and without antibiotics, and a broth culture (BACTEC 960 [Becton Dickinson, Sparks, MD] or ESP [TREK Diagnostic Systems, Cleveland, OH]). MAC isolates are identified with AccuProbe (Hologic-GenProbe, San Diego, CA).

Semiquantitative AFB smear and culture results for each submitted clinical specimen will be recorded [Wallace 1996]. Briefly, a negative culture exhibits no mycobacterial growth. Cultures will be reported as positive if growth occurs in broth medium only; growth on broth medium plus solid medium cultures with countable colonies will be reported as 0–49 colonies, 1+; solid medium growth with 50–99 colonies, 2+; solid medium growth with 100–199 colonies; 3+, solid medium growth with 200–299 colonies; and 4+, solid medium growth with at least 300 colonies. For data analysis, each culture will be scored as follows: 0, no growth in broth or solid medium; 1, broth medium growth only; 2, countable colonies (<50 colonies) on solid medium; and 3–6, 1+ to 4+ growth on solid medium, respectively.

12.5.1**Quality of life measures**

Validated instruments will be used for measurement of symptoms and quality of life. Since study subjects may have different underlying conditions, for which there are different quality of life measures, we will use a condition specific measure for each as follows:

NO-NTM

- Cystic fibrosis: Cystic fibrosis Questionnaire-Revised (CFQ-R)
- Bronchiectasis: Quality of Life – Bronchiectasis (QOL-B)
- All: St. George's Respiratory Questionnaire (SGR-Q)
- All: Leicester Cough Score

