14.1 Sample Size and Power

Planned enrollment is a minimum of 6 and a maximum of 10 subjects in this study. If a high enough proportion of subjects demonstrate a response (e.g. 5 of 6 or 6 of 8) early on in the trial, we may be able to limit the sample size, since the 95% confidence intervals would indicate a high certainty that this therapy is worth pursuing in a larger randomized controlled trial. If, however, none of the 10 subjects exhibit a response, then we can be almost certain that this particular therapy is futile, since the resulting 95% confidence interval around the response rate would range from 0% to 31%.

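### No repeat pregnancy test is scheduled between Screening and the first inhalation, and the contraception criterion ends at Day 15 while dosing runs to Day 19

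*Combined protocol and SAP*

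**What the plan says.** **Testing.** Footnote c of Table 3-1 lists the contents of the safety labs, ending with "6-GPD level, and urine pregnancy test (if applicable". The safety labs row is marked at two visits, Screening and C5 (Day 19); the A1 cell is blank. The matching exclusion in Section 10.2 reads "Positive pregnancy test at screening or" and names no later time point.

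**Contraception.** Section 10.2 also excludes women of child-bearing potential who are "Unwilling to practice a medically acceptable form of contraception from screening to Day 15".

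**Day numbering.** Section 11.1 has the gas given "by inhalation for 50 minutes three times daily on Days 1-5, 8-12, and 15-19". Section 12.4.1 uses the same calendar count: "Sputum will be collected for culture at Screening, and Days 5, 12, and 19 (treatment dates". Table 3-1 agrees, with C1 on Day 15 and C5 on Day 19. The exception is the heading of Section 9.1.2, "Treatment Period (Days 1-15", although the text beneath it describes three weeks, "each with 5 days of treatment, and 2 days off treatment in between".

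**Size.** Section 14.1: "Planned enrollment is a minimum of 6 and a maximum of 10 subjects in this study".

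**The concern.** The plan treats pregnancy as a reason not to give the gas, yet it checks for pregnancy by test only once before exposure. A pregnancy too early to show at Screening, or one that begins afterwards through contraceptive failure, would meet no further test until the last dosing day. At that point a positive result can document exposure but can hardly prevent it.

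Other entry conditions that can change in the interval are checked again. Section 10.2 applies the oxygen saturation limit at Screening or Day 1, and Section 10.1 ties clinical stability to Screening or Day 1. Pregnancy status can change in the same interval but is tied to Screening alone.

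The contraception end day raises a separate question. A site that reads Section 10.2 beside Table 3-1 would take the requirement to lapse at C1, with the rest of week C still to be dosed. What is at stake in both parts is avoidable fetal exposure to an investigational gas, not the efficacy result.

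**Working it through.** **1. Reproduce the plan's dose total, which fixes the dosing calendar (Section 11.1).**
- Daily exposure: 160 ppm × 50/60 h × 3 = 400 ppm-hours, as stated.
- Dosing days: Days 1-5, 8-12 and 15-19, so 5 + 5 + 5 = 15.
- Total: 15 × 400 = 6000 ppm-hours, as stated.
- Inhalations: 15 × 3 = 45.
- Calendar span: 5 + 2 + 5 + 2 + 5 = 19 days. The 15th treatment day is calendar Day 19.

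**2. Where the tests fall (Table 3-1).**
- Safety labs are at Screening and C5 only.
- Dosing days completed before C5: 14, so 14 × 3 = 42 of 45 inhalations have been given before C5 begins. The count is higher if the C5 sample is taken after that day's dosing starts.

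**3. Age of the Screening result at A1.**
- The window is printed as -28-14 in Table 3-1, and Section 9.1.1 gives no window. Reading it as Day -28 to Day -14 is an assumption.
- With no Day 0, the gap to Day 1 is 14 to 28 days. With a Day 0 it is 15 to 29 days.
- From A1 to C5 is a further 19 − 1 = 18 days.

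**4. Contraception end day, two readings of Section 10.2.**

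| Reading of Day 15 | Visit | Dosing days after it | Inhalations after it | Exposure after it |
|---|---|---|---|---|
| Calendar day (as in Table 3-1, 11.1, 12.4.1) | C1 | 4 of 15 (Days 16-19) | 4 × 3 = 12 of 45 | 4 × 400 = 1600 of 6000 ppm-hours |
| 15th treatment day (as the 9.1.2 heading suggests) | C5 | 0 | 0 of 45 | 0 |

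**5. How many pregnancies an A1 test might find.**
- Formula: number of subjects of child-bearing potential × annual conception rate × gap/365. A fixed lag before a test turns positive shifts the window but does not change its length.
- Assumed, because the documents give no figures: 1% to 20% conceptions per year, and a proportion of child-bearing potential anywhere from none to all of the 6 to 10 subjects.
- All of child-bearing potential, low end: 6 × 0.01 × 14/365 = 0.002.
- All of child-bearing potential, high end: 10 × 0.20 × 28/365 = 0.153.
- None of child-bearing potential: 0.
- Range for the whole trial: 0 to about 0.15.

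**The case against.** The strongest reply is that the plan is not without protection and that the numbers are tiny.

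- **A test does precede dosing.** A reader might infer from the blank A1 cell that subjects are exposed with no pregnancy test at all. The documents do not support that: the Screening test comes first and a positive result excludes. Only a repeat is missing.
- **Other checks exist.** Section 9.1.2 has subjects reviewed for changes in health and medication on A1, B1 and C1, with physical examination. Willingness to use contraception is required from Screening, so it covers the gap before A1. The investigator may exclude or withdraw a subject on judgment (Sections 10.2 and 13.2). It would therefore be wrong to say that nothing could reveal a pregnancy before Day 19. These safeguards are partial, however, and none is a test.
- **The age of the result is not established.** The 2 to 4 weeks rest on one reading of a single table cell. The absence of a test at A1 does not depend on that reading.
- **Day 15 may be harmless.** A reader might infer that the plan deliberately lets contraception stop during dosing, or that 12 inhalations are certainly uncovered. Neither follows. Read with the 9.1.2 heading, Day 15 can mean the end of treatment. The criterion concerns willingness at entry and does not tell sites to stop contraception at C1. The consent pages are not in the copy reviewed, so what subjects are told cannot be checked.
- **Frequency.** At most about 0.15 expected detections, under assumptions that push the figure up, does not support a major grade. The documents also give no data on fetal harm.

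All of this stands, and it limits the point to a minor one. It does not remove it. The A1 cell is still empty, and the sections still disagree on what Day 15 means.

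**Conclusion.** The point holds as a minor, low-cost safety correction in two parts.

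The first is firm on the text: one test before dosing, at Screening, and no repeat before A1. That the Screening result is about 2 to 4 weeks old by then depends on the assumed reading of the window.

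The second is a mismatch of wording. The calendar reading leaves 12 of 45 inhalations outside the contraception period and the treatment-day reading leaves none. Since the 9.1.2 heading appears to count 15 treatment days as if they were calendar days, a numbering slip is the more likely explanation. It is still worth correcting, because Section 10.2 defines no day count of its own and two sites must apply it.

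The case for acting rests on how little the change costs, not on how often it would matter. The conception rates behind the upper figure of 0.15 are assumptions. The sample size, the culture endpoints and their analysis are untouched.

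**What to change.** - **Table 3-1:** add a urine pregnancy test at A1, read before the first inhalation, for applicable subjects. Keep the C5 test.
- **Section 10.2, pregnancy bullet:** make a positive test at Screening or Day 1 exclusionary.
- **Section 10.2, contraception bullet:** replace Day 15 with at least Day 19 (C5). The documents give no basis for deriving a period after the last dose, so none is proposed here.
- **Section 9.1.2 heading:** change to Days 1-19, so that every section counts calendar days.

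The cost is one urine test per applicable subject at a visit that already takes place, a short wait on Day 1 for the result, a rare exclusion on Day 1, and edits to two bullets, one table row or footnote, and one heading. An A1 test still leaves the 18 days to C5 without a test, covered by contraception and the weekly health review.

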Table 15-2	Classifications for Outcome of an Adverse Event	20

Abbreviation	Definition
AE	Adverse events
ALP	Alkaline Phosphatase
ALT	Alanine transaminase
AST	Aspartate transaminase
ATS	American Thoracic Society
BCG	Bacillus Calmette-Guérin
CF	cystic fibrosis
CFF	Cystic Fibrosis Foundation
CFPPR	Cystic Fibrosis Foundation Patient Registry
CFQ-R	Cystic Fibrosis Questionnaire-Revised
CFTR	CF transmembrane conductance regulator gene
CRF	case report form
DNA	Deoxyribonucleoside acid
ECFS	European Cystic Fibrosis Society
EDC	electronic data capture
FDA	Food and Drug Association
GCP	Good Clinical Practice
GGT	Gamma-glutamyl transaminase
gNO	Gaseous Nitric Oxide
HEENT	Head, eyes, ears, nose and throat
HIPAA	Health Insurance Portability and Accountability Act
IDSA	Infectious Diseases Society of America
IND	Investigational new drug
INODD	Inhaled NO Delivery Device
INR	International normalized ratio
IRB	institutional review board
LVEF	Left ventricular ejection fraction
Mabs	Mycobacterium abscessus
MAC	Mycobacteria avium complex
MedDRA	Medical Dictionary for Regulatory Activities
metHb	Methemoglobin
MUSC	Medical University of South Carolina
NO	Nitric oxide
NO ₂	Nitrogen dioxide
O ₂	Oxygen
NTM	Non-tuberculous mycobacteria
NTM-PD	Non-tuberculous mycobacteria pulmonary disease
PPM	Parts per million
SAE	serious adverse event
SaO ₂	Arterial oxygen saturation
SAP	statistical analysis plan
SGRQ	St. Georges Respiratory Questionnaire
WHO-DD	World Health Organization Drug Dictionary

Overview of NTM lung disease

Non-tuberculous mycobacteria (NTM) have been identified as a pathogen of increasing importance in patients with cystic fibrosis (CF) [Floto 2016]. The Cystic Fibrosis Foundation Patient Registry (CFFPR) has shown prevalence rates for NTM-positive culture in the US of 12% but with considerable variation among states ranging from 0-28% [Floto 2016; Adjeman 2014]. The NTM most commonly identified in patients with CF are *Mycobacterium avium* complex (MAC) and *M abscessus* complex (Mabs) [Olivier 2003; Sermet-Gaudelus 2003].

NTM are insidious opportunistic organisms that cause lung disease in certain patient populations especially those who have cystic fibrosis (CF) but also in other populations [Honda 2015]. Although NTM could be an innocent resident in airway cultures [Martiniano 2017] there are patients in whom NTM may cause progressive lung damage leading to the diagnosis of NTM pulmonary disease (NTM-PD) [Tomashefski 1996]. There are consensus recommendations from the American Thoracic Society (ATS), Infectious Diseases Society of America (IDSA), Cystic Fibrosis Foundation (CFF), and the European Cystic Fibrosis Society (ECFS) to guide clinicians in the diagnosis and management of NTM in patients including those with CF [Floto 2016; Griffith 2007].

Treatment of NTM-PD currently involves a multidrug regimen (often 3 or more antibiotics) for prolonged durations; a frequently cited goal for treatment duration is for one year beyond conversion of cultures to negative [Griffith 2007]. These multidrug regimens have potential for intolerance and toxicity resulting in risk for suboptimal treatment and increased likelihood of antibiotic resistance. In addition, many patients will not achieve culture conversion despite adhering to their treatment regimen. There are few data available in CF patients, but overall culture conversion rates reported for other conditions are 55-65% for MAC [Wallace 1996; Tanaka 1998] and 48-58% for Mabs [Jarand 2011].

It is clear from these observations that current options for NTM-PD treatment are limited in scope and in results. An additional problem for CF patients is that the presence of Mabs in sputum cultures may create an insurmountable hurdle for eventual lung transplantation. Although the CFF/ECFS guidelines clearly state that NTM presence is not an absolute contraindication for lung transplantation [Floto 2016], there are some patients who have been declined for transplant listing because of NTM-PD. [Chalermskulrat 2006; personal communication]. Therefore, there is an urgent need for novel treatment of NTM-PD in patients with and without CF.

Overview of gNO and Rationale for Study

Recent observations of the antimicrobial effects of inhaled nitric oxide gas (gNO) suggest it may be a serious candidate for inclusion in the treatment regimen of NTM-PD. When NO molecules pass through the bacteria cell wall, they bind available thiols (e.g. glutathione) and cause cell death through a combination of asphyxiation of the electron transport complex, impairment of bacterial defense mechanisms, modification of oxygen and nitrogen radical species and metal ion deamination of its DNA [Schaefer 2006]. In vitro studies have demonstrated that NO possesses antimicrobial activity against a wide variety of bacteria, viruses, helminthes and parasites [Schaefer 2006].

Safety data: Animal studies of acute exposure to high concentrations of NO (500-1500 ppm NO) for up to 30 minutes demonstrated no acute pulmonary injury (i.e. there were no

NO-NTM

differences in histopathological evaluation between the NO-exposed animals and room air control animals). An FDA reviewer noted that, aside from the effects due to formation of methemoglobin (a known adverse effect of NO), oxidative insult to respiratory epithelia may be low/minimal at 200 ppm.

